Objectives: Primary Objective: *Define anaphylaxis rates in OFCs for peanut allergy halted by TEWL stopping rules plus standard of care clinical assessment versus control OFCs, where challenges are halted based only on clinical assessment of reaction status per standard of care.*

Secondary Objectives:

1. Define overall allergic reaction rates in peanut OFCs halted by TEWL stopping rules versus usual care.
2. Define anaphylaxis likelihood and severity via Brighton and CoFAR criteria among anaphylaxis reactions in peanut OFCs halted by TEWL stopping rules versus usual care.

Endpoints: Primary Endpoint: Anaphylaxis occurrence rate

Secondary Endpoints: Secondary endpoints will include anaphylaxis severity and overall allergic reaction rates.

Anaphylaxis likelihood will be defined by the Brighton criteria. Anaphylaxis severity will be defined via the modified CoFAR criteria (these are defined in the protocol).

Study Population: The total study population will be 40 individuals aged 6 months to 5 years, any gender, any demographic group, with a high likelihood of peanut allergy (defined in protocol). The study will take place in Michigan.

Phase: N/A

Description of Sites/Facilities This will be a single center study at the University of Michigan in Ann Arbor, MI.

[figure not shown]
Enrolling Participants:

Description of Study Intervention: This study will evaluate the use of transepidermal water loss (TEWL) continuous measurement during oral food challenge for food allergy (peanut). A stopping rule based on TEWL will be tested against usual oral food challenge care. In both cases, the standard of care will be used, where even a single symptom of an allergic reaction is used to stop oral food challenges. TEWL measures the rate of water loss from the skin in $\text{g}/\text{m}^2/\text{h}$ as a flux of water mass through an area over time.

Study Duration: 24 months

Participant Duration: Up to 9 days

Schema

Schedule of Activities

Procedures	Screening Day -7 to -1	OFC visit Visit 1, Day 1	Check-in Day 2	call,
Pre-screening questions	X			
Informed consent	X			
Confirm eligibility	X	X		
Demographics	X			
Medical history	X			
Randomization	X			
Administer study OFC		X		
Concomitant medication review	X			
Physical exam (including height and weight)		X		
Vital signs		X		
Weight		X		
Adverse event review and evaluation	X	X	X	
Complete Case Report Forms (CRFs)	X	X	X	

1. Objective

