Participants will be randomized 1:1 to the intervention and control groups. We will use permuted block randomization. We will vary the block size from 2 to 4 in order to enhance blinding. We will upload a 40-person participant list to randomization software that will produce the randomization, which will be performed at visit 1 (initial screening visit) or no later than the day of the research food challenge. The TEWL study coordinator will learn the group designation for each participant at the start of that participant's challenge by the software.

TEWL measurement methods.

All subjects will undergo continuous TEWL measurement ^{48,54}. We will use a Tewameter VT310 device (Khazaka, Germany); these probes and supporting software were supplied at no cost and with no obligation except mention of material support in publications by the manufacturer. Measurements are taken using a small adhesive to attach the probe to the skin. Measurements are taken on the volar forearm. Data are collected in MPA CT Plus software (Khazaka, Germany) which provides note-taking functions and exports data into Microsoft Excel (Seattle, WA) for analysis.

Adjudication of OFC results.

A FA physician will adjudicate reactions and diagnose anaphylaxis identically to usual care in the FA clinic. The Brighton anaphylaxis likelihood scale will be used to assess anaphylaxis likelihood. The decision tree is copied here (next page, Figure 3). The CoFAR anaphylaxis severity scale will be used for anaphylaxis severity⁷¹ and is below in the adverse event grading section of the protocol. The Brighton score gives a 0-3 score of anaphylaxis likelihood (0 = no anaphylaxis, 3 = highly likely). The CoFAR severity score gives a grade of 1-5 of anaphylaxis severity (where 1 = mild, 5 = death).

Any symptom typical of food allergy (see Brighton and CoFAR scales) will count as a reaction, consistent with standard of care diagnosis for peanut allergy. Note that this is distinct from anaphylaxis.

TEWL-based stopping rules will be applied to the intervention group. We plan to use a 1 g/m²/h increase in TEWL value averaged over the 2 minute period after a fully-consumed food dose versus the 2 minute period averaged over the period just prior to that food dose. If the individual meets this threshold, at the first sign of a clinical symptom, the food challenge will be stopped.

[figure not shown]

Figure 3: Brighton Anaphylaxis Likelihood Scale

PrePARE Trial v2.2, 30 November 2022

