We will report any adverse events and other reportable incidences and occurrences (ORIO) to the IRB. Any adverse event or ORIO will be documented of that event including a description, subject number, date, outcome, and follow-up. Reporting of adverse events and ORIOs will follow IRBMED's reporting timetable and will occur at least yearly.

Statistical Design

Stopping rules. The anaphylaxis prediction threshold used in the study 2 trial will be data-driven based on results from our ongoing data collection study. We will perform a series of logistic regression models testing the predictive value of various levels of absolute increases in TEWL, thresholds of TEWL and their combinations. These will be tested against time to first symptom, time to formal anaphylaxis diagnosis, time to first medication use, and time to epinephrine use. To avoid overfitting, these analyses will use a 2:1 derivation: validation random split. Corrections will include baseline TEWL value and variance. A minimum sustained timespan meeting the threshold (such as 30-60 seconds) may be needed to minimize the effects of noise in the measurement.

Endpoints. The primary endpoint will be anaphylaxis rate among the intervention group versus the control group and will be reported with a 95% confidence interval. Secondary endpoints will include anaphylaxis severity and overall reaction rates. Exploratory endpoints may include but are not limited to time to first treatment, time to first symptom, epinephrine use, any medication use, and time to meeting a stopping rule (regardless of whether it was implemented); all will be reported with 95% confidence intervals. Exact p-values will be calculated using Fischer's test.

Descriptive analyses. Descriptive analyses will be reported. Continuous baseline measures will be reported using either mean (or geometric mean) with 95% confidence interval or median with first and third quartiles, as appropriate. Categorical baseline and demographic characteristics and study disposition will be reported as frequencies and proportions.

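### The TEWL threshold search is checked on one 2:1 random split and is not tied to pre-symptom readings, so the rule's performance will be estimated with avoidable imprecision and its lead time is not assured

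*Combined protocol and SAP*

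**What the plan says.** The Stopping rules paragraph of Statistical Design says the threshold "will be data-driven based on results from our ongoing data collection study". The method is: "We will perform a series of logistic regression models testing the predictive value of various levels of absolute increases in TEWL", together with TEWL levels and combinations of the two. On outcomes it says: "These will be tested against time to first symptom, time to formal anaphylaxis diagnosis, time to first medication use, and time to epinephrine use". On validation it says: "To avoid overfitting, these analyses will use a 2:1 derivation: validation random split". It adjusts for baseline TEWL and its variance, and it leaves open a requirement that the threshold be sustained, with 30 to 60 seconds as an example.

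The paragraph does not give the derivation study's size or event count, the number of candidate rules, the criterion for choosing among them, a primary target, a time horizon for the logistic models, or any rule on which TEWL readings enter.

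Methodology 5.b.iv (Adjudication of OFC results) already names a rule: "We plan to use a 1 g/m²/h increase in TEWL value averaged over the 2 minute period after a fully-consumed food dose", compared with the 2 minutes before that dose. It continues: "If the individual meets this threshold, at the first sign of a clinical symptom, the food challenge will be stopped". The Synopsis says that in both arms "even a single symptom of an allergic reaction is used to stop oral food challenges".

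**The concern.** The threshold is the intervention, so the evidence that it works should be as firm as the derivation data allow. There are two separate weaknesses.

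**Validation.** A search over rises, levels and combinations needs an honest check. With one split, only a third of the children contribute to that check, and the result depends on which third was drawn.

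**Target and timing.** A single symptom stops the challenge under usual care, so TEWL adds something only through what it shows before that symptom. Anaphylaxis diagnosis, first medication and epinephrine normally come at or after it. Background reports that TEWL rises over the flare and wheal of a hive, and that it rose in one episode with hives and vomiting. If readings from after symptom onset enter the models, a rise that merely accompanies visible symptoms could be scored as prediction.

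At stake is whether the reported sensitivity and false-trigger rate can be trusted, and whether they describe a rule that acts earlier than usual care.

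**Working it through.** **The plan's own figure.** Population size assumes 80% against 30%, two-sided alpha 0.05, 80% power and Fisher's exact test. The uncorrected formula gives [1.96·√(2·0.55·0.45) + 0.8416·√(0.16 + 0.21)]² / 0.5² = 14.3, so 15 per group. With continuity correction it gives 18.1, so 19. Exact Fisher power at 19 per group is 85.2%, and 38/0.95 = 40. The stated 38 and 40 reproduce, and this point does not change them. The plan gives no figure for the precision of the threshold analysis, so the rest rests on assumptions.

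**Precision of the validated performance, by simulation.** Assumed: a normally distributed TEWL measure with means 1 SD apart, 60% events, 17 candidate cut-offs, the cut-off chosen to maximise J = sensitivity + specificity − 1, and 600 datasets per size. Error is the estimated J minus the true J of the cut-off chosen.

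| Derivation N (assumed) | Split: bias / RMSE | Bootstrap optimism correction: bias / RMSE |
|---|---|---|
| 30 | −0.01 / 0.30 | 0.04 / 0.16 |
| 60 | 0.01 / 0.21 | 0.02 / 0.11 |
| 90 | −0.01 / 0.17 | 0.02 / 0.09 |

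The ratio is about 1.9 at each size (0.30/0.16, 0.21/0.11, 0.17/0.09). With 80% events and N = 60 the RMSEs are about 0.27 and 0.15.

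**A second route.** Clopper-Pearson 95% intervals for a sensitivity near 80%, with a 50% event rate assumed:

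| N | Validation third | All children |
|---|---|---|
| 30 | 4/5: 0.28–0.99 (width 0.71) | 12/15: 0.52–0.96 (0.44) |
| 60 | 8/10: 0.44–0.97 (0.53) | 24/30: 0.61–0.92 (0.31) |
| 120 | 16/20: 0.56–0.94 (0.38) | 48/60: 0.68–0.89 (0.22) |
| 200 | 27/34: 0.62–0.91 (0.29) | 80/100: 0.71–0.87 (0.17) |

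The split interval is 1.6 to 1.7 times as wide throughout, close to √3 = 1.73. The full-data interval only approximates what resampling achieves. If 80% react with anaphylaxis, specificity rests on N/3 × 0.2 children: 2 at N = 30, 4 at N = 60, 8 at N = 120.

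**Quality of the threshold itself.** Under the 60%-event assumptions, the true J of the cut-off chosen on two thirds against all of the data is 0.332 v 0.342 (N = 30), 0.345 v 0.353 (N = 60) and 0.354 v 0.359 (N = 90). The maximum is 2Φ(0.5) − 1 = 0.383. The SD of the chosen cut-off at N = 60 is 0.50 v 0.44. The loss is about 0.01 or less.

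**Targets and timing.** Of the four targets, one is the first symptom itself and three normally come at or after it. The named rule uses 2-minute windows around a dose, whereas the finding reported in Background covers the 20 minutes after dose 1. Nothing states that the derivation used the 2-minute window or stopped at the first symptom.

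**What a weaker effect would cost.** With 80% in control and 20 per group, exact power is 84.6% at a 30% intervention rate, 65% at 40% and 41% at 50%. These figures show the sensitivity of the trial to a weaker rule. They do not estimate how much this defect would weaken it.

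**The case against.** **The split does the job it is given.** Its stated purpose is to avoid overfitting, and in the simulation it is essentially unbiased, while the bootstrap stays slightly optimistic. This stands. However, the RMSEs include that bias, and the bootstrap's total error is still little more than half as large.

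**The split does not spoil the threshold.** This also stands. A reader might infer that the threshold is badly imprecise, or that the split could by itself remove the assumed fall from 80% to 30%. A loss of about 0.01 in the true index supports neither.

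**The targets do not all follow the first symptom.** Correct: time to first symptom is the first one listed. A reader might also infer that post-symptom readings will be used. The plan is silent on this, and silence is not evidence that they will be.

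**The named rule already looks early.** A window of 2 minutes after a dose argues against a late rise in the rule as deployed. But it fixes only the deployment window. It does not show that the value was derived on that window or before symptoms, and Statistical Design still describes the threshold as something to be derived.

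**The derivation study is separate and may be complete.** Its plan is not in the documents, and Background says its data are close to publication. Its size and number of sites are not given, so calling it small or single-centre would be an assumption; the single-centre statement describes this trial. If the threshold is settled, the remedy becomes a reanalysis of existing data plus clear reporting.

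**There may be a larger obstacle to lead time.** As worded in Methodology, a child who meets the threshold is stopped at the first symptom, which appears to coincide with the single-symptom stop that the Synopsis applies to both arms. Better validation would not cure that. Those passages must be reconciled in their own right.

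**Conclusion.** The point holds in two limited parts.

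First, a single 2:1 split is an inefficient check on the searched threshold. The error in the rule's reported performance is nearly double that of bootstrap correction at N = 30 to 90, assuming 1 SD separation, 60% events and 17 cut-offs. The relative interval width (1.6 to 1.7) hardly depends on N. The absolute imprecision does, and N is not stated. The harm is to knowledge of how well the rule works, not materially to the cut-off chosen.

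Second, the plan names no primary target, requires no lead time and does not confine the models to readings before the first symptom. A threshold that offers nothing over usual care is therefore a possibility left open. The documents do not show that it has occurred.

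The sample size is unaffected.

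**What to change.** 1. Derive the threshold on all children in the derivation study. Replace the split with bootstrap optimism correction or repeated cross-validation, resampling by child and repeating the whole search over rises, levels, combinations and any sustained-duration criterion in each resample. State N, the number of events, the number of candidate rules and the selection criterion.
2. Make anaphylaxis in that challenge the primary target, using only TEWL readings before the first symptom. Keep the other three targets as descriptive.
3. Report sensitivity and false-trigger rate per child over all doses for the rule as deployed. The rule is tested after each dose, so chances of a false trigger accumulate across the challenge.
4. Reconcile Statistical Design (threshold still to be derived, possible 30 to 60 second criterion) with the 1 g/m²/h rule in Methodology, and say which text governs.

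Cost: a little more analysis code on data already being collected, with no added participants or procedures. The bootstrap keeps a slight optimism in small samples, about 0.02 to 0.05 at 60% events and up to 0.08 at 80% events with N = 30. That should be stated with the results.
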